## **Study Population**

A sample of 400 patients with HF and their caregivers (dyads, a total of 800 subjects) will be recruited using consecutive recruitment from the UAMS hospital and clinics. We will employ a rolling recruitment strategy until target sample is reached and will consistently monitor progress in recruitment.

### **Inclusion Criteria HF Participants**

- Adults aged > 55 years with HF (documented in medical record).
- Has capacity to understand informed consent.
- Able to stand (briefly) without assistance.
- Has a designated caregiver.
- Agrees to be followed (treated) by UAMS physician/provider for 6 months after discharge.
- Community dwelling

### **Exclusion Criteria HF Participants**

- Speaks a language other than English or Spanish.
- Active psychosis or other severe cognitive disorder that interferes with capacity to understand and comply with study procedures.
- A history of drug or alcohol abuse impacting their health with an emphasis on drugs that cause hemodynamic fluctuations in the past 90 days (documented in medical record by their provider).
- Currently residing or being discharged to an in-patient rehabilitation facility, Long Term Care facility or Assisted Living, and/or Hospice care.
- Current COVID + infection, or on other contact isolation.

### **Inclusion Criteria Caregivers**

- Self-identifies as a caregiver to the HF participant
- Adult 18 years of age or over

### **Exclusion Criteria Caregivers**

- Speaks a language other than English or Spanish.

Study Title: Innovative Care of Older Adults with Chronic Heart Failure (I-COACH): A Comparative Effectiveness Clinical Trial  
PI (researcher): [name], RD  
Institution: University of Arkansas for Medical Sciences  
Funding: PCORI Grant

## Risks and Benefits

A risk to study participants is the potential for loss of confidentiality of study data. Measures to protect the confidentiality of study data will be implemented as described in the Data Handling and Recordkeeping section below. Other risks to participants in this study are minimal. We will minimize risks to the participants by using procedures already being performed with the subjects for diagnostic or treatment purposes, and we will only monitor the number of provider and hospital visits via the medical record. The medical management of the HF patients will not be changed or dictated in any way by this proposed research; only the mode of delivery, and only when applicable. If the participant needs diagnostic testing or an in-person appointment as determined by the provider, we will not dissuade or intervene in any way.

All participants will receive standard education provided by the hospital and clinic providers, in addition the study staff will emphasize portions of the standard education provided regarding emergency situations that require immediate action from the patient and/or caregiver such as; hypertensive crisis, stroke signs and symptoms, and signs and symptoms of heart attack. Participants and caregivers will be instructed to take *immediate action by calling 911 or going to the local emergency department without waiting for a call from the call center.*

We have a 24-hour RN call center that mHealth participants may contact if questions or problems, or they can contact their providers as they have in the past, using standardly developed procedures, such as calling the provider's office number or the "on-call" number if after hours. The call-center has been in existence for >10 years and has highly skilled RNs that are accustomed to handling issues/problems. Participants in the provider-based model will continue with standard access to their providers.

There will be no direct benefits to the study participants; however, knowledge gained from the study could potentially benefit patients in the future.

## COVID -19 Research Guidelines

The Study Team will follow the UAMS Requirements on Human Subjects Research Studies during the COVID-19 Outbreak ( <https://tri.uams.edu/wp-content/uploads/2020/09/REVISED-Interim-UAMS-Requirements-for-Human-Subjects-Related-Research-Studies-during-COVID-19-Outbreak-051820.pdf> ). All Team members recruiting patients will be screened daily and have documented PPE training located in the Training Manual for the iCOACH study. Appropriate PPE, handwashing, and distancing will be maintained to protect our potential participants and research team

Study Title: Innovative Care of Older Adults with Chronic Heart Failure (I-COACH): A Comparative Effectiveness Clinical Trial  
PI (researcher): [name], RD  
Institution: University of Arkansas for Medical Sciences  
Funding: PCORI Grant  
per protocol. Accordingly, research visits with participants will be conducted remotely when feasible.

## **Data Handling and Recordkeeping**

The Principal Investigator will carefully monitor study procedures to protect the safety of research subjects, the quality of the data and the integrity of the study.

A study Data Management Plan (DMP) will be developed. The Team will be trained on organizing, handling and storing data per the DMP. HIPAA Privacy Rules, confidentiality and protection of human subjects will be followed according to national standards (see Human Subjects section).

Each subject is assigned a unique study code that will be used to track and manage all study data. A separate document containing the association between this unique study code and the subject's identity will be created and stored separately from the analyses dataset in a locked cabinet in the Principal Investigator's office and/or on a UAMS password-protected served accessible only by the Principal Investigator and study staff. The resulting de-identified dataset will be reviewed, descriptively analyzed, and statistically analyzed (where appropriate). Once the necessary data quality control/assurance measures have been addressed and the data analyzed, we plan to prepare the study for publication.

At the conclusion of the study, the data and data key will be stored for at least 7 years and will share data using PCORI standards by storing the de-identified final analyzable data set appropriately, and by making the full data package available to other researchers after the research is completed. We will also share de-identified results with our local UAMS supports such as the UAMS Institute for Digital Health and Healthcare Innovation and the UAMS Translational Research Institute to inform their efforts for this and other projects.

## **Data Analysis**

Data will be examined for completeness, outliers, and normality. Frequencies and percentages will be generated for screen failure reasons, for randomized participants, reasons for dropout and missing data. Descriptive statistics will be generated by intervention assignment and overall at 3 and 6 months. Baseline patient, caregiver, and system level characteristics will be compared according to intervention assignment to assess the success of the randomization; if there are imbalances, then consideration will be given to including the specific characteristic as a covariate to adjust intervention group comparisons. Continuous baseline variables will be compared using two-sample t-tests or nonparametric Wilcoxon rank sum & categorical variables will be compared using chi-square or Fisher's exact test.

Study Title: Innovative Care of Older Adults with Chronic Heart Failure (I-COACH): A

Comparative Effectiveness Clinical Trial

PI (researcher): [name], RD

Institution: University of Arkansas for Medical Sciences

Funding: PCORI Grant

For the Primary Outcome (Self-Care of Heart Failure Index, management subscale, Aim 1), we plan to compare arms in terms of change from baseline using a repeated measures mixed model analysis of covariance (ANCOVA) with an interaction between time and adjusting for baseline subscale score and other covariates such as age, race, education, and rurality. To address correlation arising from repeated measurements on the same subject over time, a random subject effect will be included in the model. For the primary endpoint, we will compare intervention effect at 3 months and at 6 months using contrasts (model-based t-tests) at a significance level of 0.025 (Bonferroni adjustment of alpha level of 0.05 for 2 comparisons). We will also use multiple imputation methods to address missing data (see below). Since scores  $> 70$  on the standardized scale have been used to indicate adequacy of self-care using a similar approach to the above, we will also analyze data as a binary endpoint in a repeated measures logistic model based on a generalized linear model framework.

Secondary Outcomes, including other patient centered, caregiver, and health system outcomes, will similarly be modeled using an ANCOVA approach. Hospital admissions and adverse events will be analyzed as proportion with unplanned admissions in the next 6 months and event rates using logistic models and models based on Poisson calculations or Negative Binomial to handle potential over-dispersion issues, and mortality and time to first unplanned hospitalization will be compared using survival methods such as log-rank tests and Cox proportional hazards models.

Evaluating heterogeneity of the treatment effect is a key consideration for Aim 2 since we want to identify which patients benefit most. The objective of the HTE analyses is evaluate whether the interventions produce differential benefits for subsets of participants. This will be investigated by including an interaction between baseline factors and intervention group (i.e., race x group) to the model above, and comparisons made using contrasts (model-based t-tests). The analytical approach taken is known as moderator analysis. Baseline factors include the demographic information as well as others measures, such as baseline self-care management score, age, race, rurality, gender, education, time since initial HF diagnosis, HF severity, depression, self-care confidence, etc. Factors with small subgroups ( $<20\%$  of the sample size) will not be investigated. If the arm x time interaction is significant, we will include 3-way interactions to investigate if the intervention effect differs by subgroup at each time point. When there is not a significant interaction with time, we will investigate how the arm effect differs for subgroups averaged across time. The proposed measures will be considered moderators if it meets the eligibility and analytic criteria described by Wang & Ware (2013). Using the model mentioned above, we will also analyze data as a binary endpoint (adequacy of self-care  $>70$  vs.  $<70$ ) in a repeated measures logistic model; with this approach we can also give the probability of achieving adequacy of self-care for various subgroups in addition to odds ratios.

Study Title: Innovative Care of Older Adults with Chronic Heart Failure (I-COACH): A

Comparative Effectiveness Clinical Trial

PI (researcher): [name], RD

Institution: University of Arkansas for Medical Sciences

Funding: PCORI Grant

Investigation of mediators (SCI-2) will be done by examining whether changes in self-care confidence, self-efficacy to manage symptoms, self-efficacy to manage

medications & treatment, or HF knowledge mediate the effect of the mHealth intervention on patient outcomes (e.g., self-care of HF index). We will use the method proposed by Hayes (2016) for evaluating mediation effects via a regression modeling approach which reflects the change scores in the mediators. Baseline measurement of the potential mediator and baseline outcome measure (e.g., self-care of HF index) will be included as covariates to provide a precise estimate of mediation effects. The test of mediation evaluating the indirect effect of the invention on outcome will be based on a product of coefficients approach. The modeling and testing for mediation as described by Hayes (2016) will be done for each mediator separately. As a sensitivity analysis for the mediation analyses, we plan to use a non-parametric bootstrap approach. Both the indirect effect of each mediator along with 95% bootstrap confidence intervals will be reported.

Sensitivity analyses to determine the impact of key assumptions. In the event that continuous endpoints are skewed or key distributional assumptions are not met, we will investigate transformations (e.g., log) and compare findings based on parametric and non-parametric tests (e.g., Wilcoxon rank-sum test & robust regression techniques), as a sensitivity analysis to confirm findings. To address the impact of missing data, multiple imputation methods will be investigated.

Plans to address missing data. Data collection procedures will be designed so that measures/instruments will not allow subjects to skip questions and assistance will be available to help complete the survey, if needed (e.g. may need to read to some participants if vision is problematic). We have built in travel resources to visit participants' homes to complete a measurement interval (baseline,-3,-6 month), and/or can split this task within 2 days if participants become fatigued, as needed. See Data Collection Procedures. Sensitivity analyses will be conducted to investigate the impact of missing data (in the case of attrition) on estimates. The above analyses based on mixed models assume data are missing completely at random, but we will also use multiple imputation techniques to model missing data patterns, which is appropriate when data are not missing at random. These results will be reported as well in keeping with an intent-to-treat approach which uses data from all randomized participants, even those lost to follow-up. We anticipate that up to 10% of participants may die by six months. To address any differential dropout rates between interventions, the composite endpoint approach will be assessed similar to what was done for QOL outcomes in the ELITE study; one-sided tests are required for the approach so we will split our alpha accordingly assuming the alternative hypothesis is that the enhanced mHealth care model results in better outcomes.

Study Title: Innovative Care of Older Adults with Chronic Heart Failure (I-COACH): A Comparative Effectiveness Clinical Trial  
PI (researcher): [name], RD  
Institution: University of Arkansas for Medical Sciences  
Funding: PCORI Grant

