### **Language**

Instruments will be provided for English and Spanish-speaking patients, may be read to the participants if desired, and will be installed with large print and/or an easy-to-use format loaded on the tablet device. Outcome data/measures for the provider and hospital system will be obtained from the electronic medical record and hospital computer database within 30 days after the 6-month follow-up measures have been completed.

Study Title: Innovative Care of Older Adults with Chronic Heart Failure (I-COACH): A Comparative Effectiveness Clinical Trial  
 PI (researcher): [name], RD  
 Institution: University of Arkansas for Medical Sciences  
 Funding: PCORI Grant

**Table 1. Specific Aim Addressed, Measure, Outcome Type, Purpose of Measure, Administration Interval & Estimated Participant Completion Time**

SP. AIM	Measure	Outcomes	Purpose of Measure	Base line	3 mth	6 mth	Completion Time
PATIENT CENTERED OUTCOME MEASURES							
1a	Self-Care of HF Index v7.2	Primary Outcome:	Assess self-care management, symptom perception & maintenance skills	X	X	X	8 min.
3	Self-Care Confidence 	Hypothesized Mediator:	Assess confidence in ability to care for self	X	X	X	3-5 min.
3	Promis® Self-Efficacy to Manage Symptoms 	Hypothesized Mediator:	Assess ability to manage symptoms for chronic conditions	X	X	X	15-20 min.
3	Promis® Self-Efficacy to Manage Medications & Treatments 	Hypothesized Mediator:	Assess ability to manage medication & treatments for chronic conditions	X	X	X	20 min.
3	Dutch HF Knowledge Scale 	Hypothesized Mediator	Assess Knowledge of HF	X	X	X	5 min
1a & 2	Promis® 43v2.1 Health profile 	Secondary Outcome Patient Characteristics	Assess physical function, anxiety, depression, fatigue, sleep, social roles, and pain	X	X	X	10-20 min.
1a	Health Distress 	Secondary Outcome Patient Characteristics	Assess psychological impact/health distress	X	X	X	1-3 min
1a	Promis® Informational Support v 2.0 6a 	Secondary Outcome	Assess perceived availability of helpful information or advice	X	X	X	2-4 min.
1a	System Usability Scale 	Secondary Outcome	Ease of using the technology		X	X	3-5 min.

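### The primary model's covariates may depend on between-arm baseline tests added to an open list; separately, the lone random subject effect would normally pool the 3- and 6-month variances

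*Combined protocol and SAP*

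**What the plan says.** All the relevant text is in the Data Analysis section.

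- **Baseline comparison.** "Baseline patient, caregiver, and system level characteristics will be compared according to intervention assignment to assess the success of the randomization". For continuous measures, "Continuous baseline variables will be compared using two-sample t-tests or nonparametric Wilcoxon rank sum"; categorical measures get chi-square or Fisher's exact tests. No level for declaring an imbalance is given.
- **Consequence of an imbalance.** "if there are imbalances, then consideration will be given to including the specific characteristic as a covariate to adjust intervention group comparisons". The primary comparison is not exempted.
- **Primary model.** A repeated measures mixed model ANCOVA of the self-care management subscale, "adjusting for baseline subscale score and other covariates such as age, race, education, and rurality". The words introducing the examples leave the list open.
- **Within-subject correlation.** "a random subject effect will be included in the model". No residual covariance structure is named.
- **Primary tests.** "we will compare intervention effect at 3 months and at 6 months using contrasts (model-based t-tests) at a significance level of 0.025", which is a Bonferroni split of 0.05.

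Nothing elsewhere closes the covariate list or names a covariance structure. The randomization text states no stratification factors that would settle the covariates. The rank-based and robust methods described later in the section are offered only "as a sensitivity analysis to confirm findings".

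**The concern.** **Covariates.** After sound randomization, any baseline difference is due to chance. A between-arm p-value therefore says nothing about whether a variable predicts self-care management, which is the reason to adjust for it. The plan uses that p-value as a trigger, sets no threshold, and does not say what follows from giving a variable consideration. Two analysts who follow the text faithfully on the same data could report different primary estimates. At stake is whether the primary estimate comes from one model fixed in advance.

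**Covariance.** A random subject effect with the usual single residual variance implies the same total variance at both visits. Each visit nevertheless has its own primary test. If the true SDs differ, the standard error is too large at one visit and too small at the other, so the two separate claims are not each tested at the stated level. This point is secondary and conditional on unequal SDs.

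**Working it through.** **Plan's own figure.** 0.05 / 2 = 0.025 per visit, as stated. Taken as two-sided (an assumption), the critical value is z = 2.2414. The documents give no SD, R² or imbalance threshold, so those inputs below are assumptions.

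**1. Shift from one flagged covariate.** Assume the covariate just reaches significance at 0.05 (z = 1.96) and has partial R² of 0.02 to 0.05 with the outcome, given the other covariates.

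- Shift in standard errors = √R² × 1.96: √0.02 × 1.96 = 0.28 and √0.05 × 1.96 = 0.44.
- If the shift weakens a contrast at p = 0.025: 2[1 − Φ(2.2414 − 0.277)] = 0.050 and 2[1 − Φ(2.2414 − 0.438)] = 0.071.
- If it strengthens it: 2[1 − Φ(2.2414 + 0.277)] = 0.012 and 2[1 − Φ(2.2414 + 0.438)] = 0.007.
- Including the covariate also multiplies the standard error by √(1 − R²), a fall of 1.0% to 2.5%. Dividing the shifted z by that factor changes the weakened values to 0.047 and 0.064. Allowing also for the collinearity between arm and an imbalanced covariate (n = 400) gives 0.048 and 0.066.

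The range is therefore roughly 0.05 to 0.07 one way and about 0.01 the other.

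**2. Type I error of a mechanical rule.** Null simulations used 180 patients per arm (400 patients, assumed 1:1 allocation, less the 10% deaths that the plan anticipates), with 6,000 runs and a nominal level of 0.025. Adding every covariate flagged at 5% gave a rejection rate of 0.026 (4 candidates, total R² 0.2) and 0.020 (10 candidates, total R² 0.3). With all candidates fixed in advance the rates were 0.028 and 0.024. Monte Carlo error is about 0.002, so a mechanical rule shows no inflation.

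**3. How often something is flagged.** Table 1 marks 16 rows at baseline, or 15 without the primary index. With one test per row at 0.05, the chance of at least one flag is 1 − 0.95^15 = 54% if the rows are independent; by simulation it is 46% at correlation 0.3 and 36% at 0.5. This shows only that the discretionary step is likely to arise. It is not the chance that the primary estimate moves.

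**4. Pooled variance.** With complete data, the pooled SD is √[(s₃² + s₆²)/2]. Actual alpha at a visit with SD s is 2[1 − Φ(2.2414 × pooled/s)]. Power, for an effect that would have 80% under the visit's own SD, is Φ(2.2414 + 0.8416 − 2.2414 × pooled/s). Family-wise error is from the bivariate normal at correlations 0.3 to 0.7.

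| Assumed SD, 3/6 months | Pooled SD | Alpha, 3/6 months | Power, 3/6 months | Family-wise error |
|---|---|---|---|---|
| 20/20 | 20.00 | 0.025/0.025 | 80%/80% | 0.043–0.048 |
| 19/21 | 20.02 | 0.018/0.033 | 76%/83% | 0.044–0.049 |
| 18/22 | 20.10 | 0.012/0.041 | 72%/85% | 0.047–0.052 |

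If the larger SD is at 3 months, the columns swap. A single random-intercept fit at an SD ratio of 1.5 confirmed the mechanism: the standard error was 0.134 at both visits, against 0.107 and 0.156 when each visit was analysed alone.

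**5. Cost of separate variances when the SDs are equal.** With about 400 patients, the t critical value rises from 2.2457 (780 df) to 2.2501 (390 df), and power falls from 79.9% to 79.8%.

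**The case against.** The strongest reply is that the consequences are small. The imbalance step looks at baseline data rather than outcomes, is not binding, and adds to a sensible named core. Applied mechanically, it leaves type I error alone. All of this stands, and it limits the weight of the point. It does not make the primary model prespecified.

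A reader might infer that the plan inflates type I error. In the simulations above, reporting the most favourable of the unadjusted, flagged-only and fully adjusted models raised the rejection rate to 0.041 against 0.025. But the plan describes no choice among models after outcomes are seen, so that figure cannot be charged to it.

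A reader might also take 54% as the chance of a changed result. That would need a flag on a variable outside the named list, prognostic value beyond the baseline score, and a decision to include it. No joint probability can be derived from the documents. The row count is also crude: the demographics row includes education and rurality, which the model already names, and the PROMIS-43 row covers seven domains.

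On the covariance, calling the model repeated measures does not rule out visit-specific variances, and the SDs used here are assumed. That is correct. If such variances are intended, one sentence settles the matter. It would also be wrong to read the pooled model as a plain loss of power, because what one visit loses the other gains.

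**Conclusion.** The covariate point holds on the text alone: the primary model is not fully fixed, and the stated trigger for changing it is unrelated to prognosis. Its size is illustrative and rests on an assumed partial R² of 0.02 to 0.05 and a covariate just at the 5% level: about 0.3 to 0.4 standard errors in either direction, enough to change the conclusion of a borderline contrast. The documents support neither a claim of type I error inflation nor one of a large power effect; fixing the list gains only 1.0% to 2.5% in standard error per such covariate.

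The covariance point holds only if the visit SDs differ and the usual single residual variance is used. Any harm then falls on the separate 3- and 6-month claims, since family-wise error stays at 0.044 to 0.052 for the unequal SDs tried. Equal SDs give no distortion. Together these make a minor to moderate improvement that is cheap to adopt.

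**What to change.** Amend the Data Analysis section before arm-level data are examined:

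1. State the primary covariates as a closed list of those already named (baseline management score, age, race, education and rurality), with the coding of each.
2. Report the baseline table descriptively, without between-arm tests.
3. Confine any imbalance-driven adjustment to a labelled sensitivity analysis.
4. Fit the arm-by-time model with an unstructured 2x2 residual covariance for the 3- and 6-month scores in place of the lone random subject effect, and name the degrees-of-freedom method.

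The cost is SAP wording and one extra covariance parameter (three instead of two). All the variables are already collected. If the SDs turn out equal, the loss is about 0.1 percentage point of power.

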## Specific Aims and Hypotheses

### Aim 1.

The principle aim of our proposed clinical trial is whether an enhanced *mHealth care management model* with connected health technology used in partnership with the healthcare system team, an older person with heart failure (HF), and their caregiver are more effective than a *provider directed management model* using non-connected home equipment kits. Self-care of HF, quality of life and quality care are represented by multiple outcome measures that are important to patients, caregivers and healthcare (HC) systems. Specifically,

**Aim 1a. Patient-centered outcome measures:** We hypothesize that the mHealth model will increase measures from baseline to 3- and 6-month for the primary outcome of self-care management of HF compared to the provider-directed model. Further, we hypothesize that the mHealth model will increase measures from baseline to 3- and 6-month for secondary outcomes of Self-efficacy to manage symptoms, medications, & treatments; self-care confidence; physical function, sleep, social roles, (Promis 43v2.1 Health profile); heart failure knowledge; satisfaction with care; quality of life; informational support and equipment usability (3 and 6 months), while decreasing health distress, anxiety, depression, fatigue, and pain compared to the provider-directed model.

**Aim 1b. Caregiver outcome measures:** We hypothesize that the mHealth model will reduce caregiver burden, while increasing caregiver health compared to the provider-directed model from baseline to 6-months.

**Aim 1c. Health system outcome measures:** We hypothesize that the mHealth model will reduce hospital admissions, 1-month readmissions, emergency department

Study Title: Innovative Care of Older Adults with Chronic Heart Failure (I-COACH): A Comparative Effectiveness Clinical Trial  
PI (researcher): [name], RD  
Institution: University of Arkansas for Medical Sciences  
Funding: PCORI Grant

visits, and 6-month mortality of HF participants while increasing satisfaction with care, compared to the provider-directed model.

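### The two primary contrasts are each held at a fixed 0.025; Holm's procedure at the same family-wise 0.05 keeps every Bonferroni rejection and can also support the second visit

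*Combined protocol and SAP*

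**What the plan says.** For the primary outcome the Data Analysis section fits a repeated-measures mixed model and tests the difference between arms by a separate contrast for each of the two follow-up visits. The alpha rule for these tests is: "at a significance level of 0.025 (Bonferroni adjustment of alpha level of 0.05 for 2 comparisons". Each visit's threshold is therefore 0.025 whatever the other visit shows. No step-down, hierarchical or alpha-recycling rule appears anywhere in the document.

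Aim 1a hypothesises that "the mHealth model will increase measures from baseline to 3- and 6-month for the primary outcome of self-care management of HF", so both visits belong to the stated hypothesis.

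The section does not say whether the primary contrasts are one- or two-sided. One-sided testing is mentioned only for the composite-endpoint analysis of differential dropout: "one-sided tests are required for the approach so we will split our alpha accordingly".

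**The concern.** Splitting alpha over two visits treats each visit as a claim in its own right. For two separate claims, plain Bonferroni is not the most powerful simple rule at the level the plan has chosen. Once one visit is significant at 0.025, at most one true null remains, and the full 0.05 can be used on it without raising the family-wise error above 0.05. The plan leaves that alpha unused.

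The loss falls on whichever visit has the weaker result. If the effect takes time to build or fades, that visit could be significant at 0.05 and still go unclaimed, although Aim 1a covers it.

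**Working it through.** **1. The plan's own figure.** 0.05 / 2 = 0.025, as stated. The two levels sum to 0.05. If the tests were independent, the family-wise error would be 1 - 0.975² = 0.0494. Positive correlation lowers it. The stated rule is valid.

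**2. Holm keeps the same level.** If both nulls are true, an error requires the smaller p to be at most 0.025, with probability at most 0.025 + 0.025 = 0.05. If one null is true, rejecting it requires its own p to be at most 0.05, with probability at most 0.05. Neither step uses the correlation.

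**3. Where the rules differ.** Every p at or below 0.025 is rejected by both rules. They differ only when one p is at most 0.025 and the other lies above 0.025 and up to 0.05. Example: p = 0.01 and 0.04 gives one visit under Bonferroni and two under Holm.

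**4. Inputs for the illustration.**
- Sample size: "A sample of 400 patients with HF and their caregivers" (Study Population). Equal arms are assumed, because the allocation ratio is not stated.
- Loss: "We anticipate that up to 10% of participants may die by six months" (Data Analysis, missing data). Applied to both visits: 200 × 0.9 = 180 per arm.
- Effect in SD units, correlation of the two contrasts (0.3 to 0.7) and two-sided testing are assumptions; the documents give none of them.

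**5. Formulas.** Each contrast has a z-statistic with mean d × √(n/2). Two-sided critical values are 2.2414 (0.025) and 1.9600 (0.05). Holm power at visit 1 = P(reject 1 at 0.025) + P(reject 1 at 0.05 and 2 at 0.025) - P(reject both at 0.025).

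For d = 0.30 and n = 180, the mean is 0.30 × √90 = 2.846, and Bonferroni power at a visit is Φ(2.846 - 2.2414) = 72.7%. With equal effects, power at a given visit is half the sum of P(at least one) and P(both). At correlation 0.5, from 2,000,000 simulated draws:
- Bonferroni: (0.8637 + 0.5908) / 2 = 0.727
- Holm: (0.8637 + 0.6942) / 2 = 0.779

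**6. Results, two-sided, 180 per arm, correlation 0.3 to 0.7.**

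| Effect at 3 / 6 months (SD) | Quantity | Bonferroni | Holm |
|---|---|---|---|
| 0.20 / 0.20 | given visit | 36.5% | 40.7-40.8% |
| 0.25 / 0.25 | given visit | 55.2% | 60.2-60.8% |
| 0.30 / 0.30 | given visit | 72.7% | 77.4-78.3% |
| 0.40 / 0.40 | given visit | 94.0% | 95.9-96.3% |
| 0.50 / 0.50 | given visit | 99.4% | 99.7% |
| 0.30 / 0.30 | both visits | 56-62% | 68-72% |
| 0.30 / 0.30 | at least one visit | 83-89% | 83-89% (identical) |
| 0.35 / 0.25, either order | weaker visit | 55.2% | 64.4-64.8% |
| 0.35 / 0.25, either order | stronger visit | 86.0% | 86.8-88.1% |

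**7. Sensitivity.**
- 160 per arm: given visit at 0.30 SD 67.1% to 72.0-72.8%; weaker visit (0.35 / 0.25) 49.8% to 58.8-59.4%.
- 200 per arm: 77.6% to 81.9-82.8%, and 60.2% to 69.3-69.7%.
- One-sided tests, 180 per arm: 81.2% to 85.5-86.5%, and 66.0% to 75.5-75.7%.

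**8. Error.** With no effect at either visit, the family-wise error is 4.3-4.8% under both rules. With no effect at one visit, the error there rises from 2.5% to 3.9-4.2% when the other effect is 0.30 SD, and to 4.9-5.0% when it is 0.50 SD. It cannot exceed 5%.

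**The case against.** Nothing in the plan is wrong: it pre-specifies a valid rule, and replacing one valid rule with another is close to preference. That stands, and it is why this is an optional improvement.

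The gain also depends on reading the visits as two separate claims. If one significant visit is enough, Holm adds nothing. If both were required jointly, each could be tested at 0.05 with no adjustment, and Holm would not be the remedy. The documents do not define success. However, a Bonferroni split over two visits makes sense only if each can be claimed by itself, so separate claims is the reading that fits the plan.

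The power figures rest on assumptions. Six-month deaths are applied to the 3-month visit as well, and because the model adjusts for baseline, the relevant SD is the adjusted residual SD. These affect the size of the gain. They do not affect its direction, which follows from steps 2 and 3 alone.

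Bonferroni also offers simple 97.5% intervals that always agree with the tests. Under Holm, the second contrast's 97.5% interval could include zero although the test rejects. This is the best reason to keep the current rule. Against it, the plan names no intervals for the primary contrasts; the only ones it specifies are for mediation ("Both the indirect effect of each mediator along with 95% bootstrap confidence intervals will be reported").

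**Conclusion.** The point holds as an efficiency gain at no cost in family-wise error. That Holm rejects at least as much as Bonferroni is certain and needs no assumption about effect, correlation, sample size or sidedness.

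The size is illustrative. At 180 per arm with two-sided tests, the gain at a given visit is about 0.3 to 5.6 percentage points when effects are equal (0.20 to 0.50 SD), and about 9 to 10 points at the weaker visit under the assumed 0.35 / 0.25 SD pattern. There is no gain in the chance of at least one significant visit, so this is not a gain in overall trial success. It is a low-priority change that the team could make.

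**What to change.** Replace the significance rule for the primary contrasts with:

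> *The 3- and 6-month contrasts will be tested by Holm's procedure at family-wise alpha 0.05 (smaller p-value at 0.025; if significant, the other at 0.05), using [one- / two-]sided tests.*

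The team must fill in the sidedness, which is currently unstated. It would also help to confirm that the visits are separate claims, and to say whether the multiple-imputation and composite analyses follow the same rule.

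The change must be made before outcome data are examined by arm; adopting Holm after seeing a p-value such as 0.04 would not be credible.

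The cost is one sentence, with no extra patients, visits or data. The downsides are less simple matching intervals, and an error at a single null visit that can rise from 2.5% to at most 5%, still within the plan's 0.05.
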